## Definitions of Terms

Term	Definitions
Study period	From the day of informed consent to the final day of the follow-up observation period
Treatment period	From the first day of the treatment period to the final day of the treatment period
Day of completion of treatment period	Week 52 of the treatment period or the day of discontinuation during the treatment period
X weeks prior to the first day of the screening period	Same day of the week X weeks prior to the first day of the screening period
MT-6548 tablets	Each film-coated tablet containing 150 mg of vadadustat
Correction cohort	Patients who have not received ESA formulations from 8 weeks prior to the first day of the screening period
Conversion cohort	Patients who have received the same ESA formulations from 8 weeks prior to the first day of the screening period

## 1. Introduction

This is a document that shows more detailed contents in addition to those of the study plan on the statistical analysis protocol for the efficacy and safety of “A Phase III, Open-label Study of MT-6548 in Peritoneal Dialysis Subjects with Anemia Associated with Chronic Kidney Disease in Japan.”

## 2. Study Objectives and Study Design

### 2.1 Study objectives

[figure not shown]
The purpose of the study is to evaluate the efficacy and safety of MT-6548 in patients with anemia associated with chronic kidney disease undergoing peritoneal dialysis.

### 2.2 Study design

Study phase: Phase III

Study type: Confirmatory study

Multicenter, uncontrolled, open-label study

Evaluation time point

Item	VISIT	Informed consent	Screening period [a]		Treatment period											Final day of follow-up observation period [b]
			First day	Visit 2	First day [c]	W2	W4	W6	W8	W10	W12	W16	W20	W24	Day of discontinuation	
Visit no.	IC	SV1	SV2	TV1	TV2	TV3	TV4	TV5	TV6	TV7	TV8	TV9	TV10	TV11	FU	
Permitted range (day)	-	-	-	-	±3	±3	±3	±3	±3	±3	±7	±7	±7	+ 7 or + 14 [d]	+7	
Procedure/evaluation																
Informed consent	X															
Inclusion/exclusion criteria	X	X	X	X												
Patient's background and history	X			X												
Height				X												
Body weight (weight excluding dialysis solution)				X						X			X	X		
Folic acid and vitamin B 12		X														
Pregnancy test [e]		X											X	X		
Haematology test		X	X [f]	X	X	X	X	X	X	X	X	X	X	X	X	
Blood biochemistry test		X		X	X	X	X	X	X	X	X	X	X	X	X	
C-reactive protein		X		X									X	X		
Iron-related measures		X		X	X	X	X	X	X	X	X	X	X	X	X	
Hepcidin				X	X	X	X			X			X	X		
Erythropoietin				X	X	X	X			X			X	X		
VEGF				X						X			X	X		
Urinalysis (qualitative)		X		X	X	X	X	X	X	X	X	X	X	X	X	
Vital signs [g]		X		X	X	X	X	X	X	X	X	X	X	X	X	
12-lead ECG [h]				X									X	X		
Fundoscopy [d]			X										X	X		
Chest X-ray [d]			X										X	X		
QOL measures (EQ-5D-5L, KDQOL)				X						X			X	X		
AE investigations				X	X	X	X	X	X	X	X	X	X	X	X	
Blood sampling for genetic analysis [i]					Blood sampling should be performed once as early as possible after 2 weeks of											
Drug evaluation/procedure																
Investigation of concomitant drugs				X	X	X	X	X	X	X	X	X	X	X	X	
Prescribing MT-6548 tablets [j]				Administration according to the dosage adjustment guideline												
Administration of iron supplements				Administer iron supplements to maintain serum ferritin values ≥100 ng/mL or TSAT ≥20%.												

- [a] The screening period can be up to 6 weeks. Test results should be reviewed prior to transition from the first day of the screening period to screening period Visit 2 and from screening period Visit 2 to the first day of the treatment period. Re-testing can be performed as necessary.
- [b] Not required if withdrawing prior to the treatment period
- [c] Should be performed prior to study drug treatment (adverse event [AE] investigations begin after study drug treatment)
- [d] Fundoscopy and chest X-ray should be performed once during the screening period. Fundoscopy and chest X-ray performed once during Weeks 20–24 of the treatment period. Should be performed within 14 days of study withdrawal if treatment is discontinued.
- [e] Only female subjects who may have pregnant potential.
- [f] Only Hb levels should be measured.
- [g] Measurements should be made before blood sampling as much as possible. Measurements should be made in the sitting position after 5 minutes of rest.
- [h] Measurements should be made before blood sampling as much as possible. Measurements should be made in the supine position after 5 minutes of rest.
- [i] Blood should be collected once as early as possible after Week 2 of the treatment period for subjects who have given consent to the genetic analysis tests.
- [j] MT-6548 tablets should be prescribed to subjects depending on the number of their unused tablets. Subjects should be instructed to use up one bottle before opening the next.

### 2.3 Rationale for sample size

Forty subjects will be enrolled in the treatment period

#### [Rationale]

If the standard deviation of the mean Hb value, which is one of the efficacy endpoints of this study, is assumed to be 1.78 based on the upper limit of the two-sided 80% confidence interval in the MT-6548 300 mg group at the end of the primary efficacy evaluation period (Week 6) in a dose-finding study in Japanese patients with anemia associated with NDD-CKD (Study CI-0021), a sample size of 40 subjects allows value estimation with an accuracy of mean  $\pm 0.57$  g/dL (95% confidential interval [CI]). “Guidelines for the Treatment of Renal Anemia in Patients with Chronic Kidney Disease (JSDT 2015)” shows that Hb values vary in a range of about 1 g/dL in normal clinical contexts, which seems to indicate that the evaluation with the clinical significance is possible by estimating mean Hb values with an accuracy of mean value  $\pm 0.57$  g/dL (95% CI). A sample size of 40 subjects should also enable analysis of safety.

### 3. Endpoints

#### 3.1 Efficacy endpoints

##### 3.1.1 Primary endpoint

- (1) Mean Hb values at Weeks 20 and 24 of the treatment period
- (2) Hb value at each timepoint in the treatment period
- (3) Proportion of subjects with mean Hb values within the target range (11.0–13.0 g/dL), <11.0 g/dL, and  $\geq$ 13.0 g/dL at each time point in the treatment period

##### 3.1.2 Other endpoints

- (1) Proportion of subjects receiving rescue therapy with ESA formulations, red blood cell transfusion, or phlebotomy
- (2) Study drug dosage
- (3) Total number of study drug dosage adjustments
- (4) Iron supplement dosage
- (5) Proportion of subjects receiving oral, intravenous, or (any route) administration of iron supplements
- (6) Proportion of subjects with serum ferritin  $\geq$ 100 ng/mL or TSAT  $\geq$ 20%.
- (7) Changes and rate of changes in iron-related indices (serum iron, TIBC, TSAT, and serum ferritin levels) and hepcidin from the first day of the treatment period
- (8) Changes in hematocrit, red blood cell count, reticulocytes (number and rate), mean corpuscular volume, mean corpuscular hemoglobin, and erythropoietin from the start of the treatment period
- (9) Changes and rate of changes in systolic blood pressure, diastolic blood pressure, lipids (total cholesterol, LDL-C, HDL-C, LDL-C/HDL-C ratio, triglycerides), and blood glucose from the start of the treatment period
- (10) QOL indices (EQ-5D-5L, KDQOL)

#### 3.2 Safety endpoints

- (1) Adverse events and adverse drug reactions
- (2) Laboratory test values
  - 1) Hematology tests:

Mean corpuscular volume, mean hemoglobin, mean hemoglobin concentration, RBC distribution width, WBC count, WBC fractions (neutrophils, eosinophils, monocytes, lymphocytes, basophils), platelet count

- 2) Blood biochemistry tests:

Total protein, albumin, blood glucose, urea nitrogen, creatinine, uric acid, CPK, total bilirubin, AST, ALT, ALP, LDH,  $\gamma$ -GTP, Na, K, Cl, Ca, P, Mg, bicarbonate, total cholesterol, LDL-C, HDL-C, triglycerides

- 3) C-reactive protein
  - 4) Folic acid and vitamin B12
  - 5) Vascular endothelial growth factor (VEGF)
  - 6) Urinalysis (qualitative)
- Glucose, protein, urobilinogen, occult blood
- (3) Resting standard 12-lead ECG
  - (4) Body weight (body weight excluding dialysate weight)
  - (5) Vital signs
  - (6) Fundoscopy
  - (7) Chest X-ray
  - (8) Proportion of subjects with documented Hb values of  $\geq 13.0$  g/dL or  $\geq 14.0$  g/dL
  - (9) Proportion of subjects with documented Hb values of  $< 9.0$  g/dL or  $< 8.0$  g/dL.
  - (10) Proportion of subjects with a documented Hb value increase rate of  $> 0.5$  g/dL/week
  - (11) Hb value after dose reduction or interruption of the study drug

## 4. Definition of Derived Variables

### 4.1 Age at informed consent

Age (year) = Date of informed consent (year) – Date of birth (year)

However, when (Date of informed consent [month] < Date of birth [month]) or (Date of informed consent [month] = Date of birth [month] and Date of informed consent [days] < Date of birth [days]), 1 is subtracted from the traditional Japanese age system calculated above.

### 4.2 Duration of disease

The duration of disease (year) should be the period from the onset of renal anemia to the consent month and shall be the integer part + 1 digit (rounded). Duration of disease is calculated as follows:

Duration of disease (year) = (Date of consent acquisition [year] – Time of onset [year]) + (Date of informed consent [month] – Time of onset [month])/12

If the month of onset is unknown, the month is calculated as 1.

### 4.3 Period from the start of peritoneal dialysis

The period from the start of peritoneal dialysis (year) should be the period from the start of peritoneal dialysis to the month of consent acquisition and should be the integer part + 1 digit (rounded). The period from the start of peritoneal dialysis is calculated as follows: Period from the start of peritoneal dialysis (year) = (Date of consent acquisition [year] – Start of peritoneal dialysis [year]) + (Date of consent acquisition [month] – Start of peritoneal dialysis [month])/12

If the month of start is unknown, the month is calculated as 1.

#### 4.4 BMI

$BMI (kg/m^2) = \text{Body weight (body weight excluding dialysate weight) (kg)} / (\text{Height [m]})^2$

Should be rounded and displayed to one decimal place.

#### 4.5 LDL-C / HDL-C ratio

$LDL-C / HDL-C \text{ ratio} = LDL-C (mg/dL) / HDL-C (mg/dL)$

Should be rounded and displayed to two decimal places.

#### 4.6 Number of days of drug interruptions

The number of days of drug interruptions does not include subject's missing to take the drug and is defined by the following formula. Number of days of drug interruptions (days) = Day of resumption of study drug administration – First day of study drug interruption

If there are multiple interruptions, the sum of them should be used.

Resumption day of study drug administration: After the entry of "Daily Dose" = 0 mg, the first dose should be taken when a value of >0 mg is entered for the first time. If the drug interruption continues until Week 24 of the treatment period, days should be calculated based on the visit date after Week 24 of the treatment period as the resumption date. However, if the treatment is completed or discontinued while the drug interrupted, the day of blood sampling for hematology tests at Week 24 or the day before the discontinuation of treatment should be used.

First day of study drug interruption: First day of administration when "Daily Dose = 0 mg is first entered in the CRF.

#### 4.7 Duration of study drug administration

For subjects who completed treatment period:

Duration of study drug administration (days) = Day of blood sampling for hematology tests at Week 24 – First day of the treatment period

For subjects who discontinued: Duration of study drug administration (days) = Day of discontinuation – First day of the treatment period

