## 8.4 Treatment period

From the first day of the treatment period to the day prior to Week 24 of the treatment period.

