[e] Only female subjects who may become pregnant.

[f] Hb only measured.

[g] Measured to extent possible prior to blood sampling. Measured with subject sitting after 5 minutes of rest.

[h] Measured to extent possible prior to blood sampling. Measured with subject in supine position after 5 minutes of rest.

[i] Blood sampling for genetic analysis performed once as early as possible after Week 2 of treatment period in subjects who have granted consent.

[j] Prescribe MT-6548 Tablet depending on quantity of subject's remaining study drug. Subjects are instructed to open new bottles of study drug only after completing previous bottle.

If tests and observations cannot be performed on the scheduled day, they may be performed within the permitted ranges shown below.

Table 9.1-1 Permitted ranges for study center visits

Evaluation timepoint		Reference date	Permitted range
Screening period *1	Initiation date	–	–
	Visit 2	–	–
Treatment period	First day *2	Day 0	–
	Week 2	Day 14	Day 11–17
	Week 4	Day 28	Day 25–31
	Week 6	Day 42	Day 39–45
	Week 8	Day 56	Day 53–59
	Week 10	Day 70	Day 67–73
	Week 12	Day 84	Day 81–87
	Week 16	Day 112	Day 105–119
	Week 20	Day 140	Day 133–147
	Week 24	Day 168	Day 161–175
Day of discontinuation of treatment		Day of discontinuation	Within 7 days of discontinuation *3
Follow-up observation period	Day of completion	Week 24 of treatment period (or day of discontinuation of treatment period)	14–21 days

\*1: Maximum screening period length is 6 weeks. Re-testing may be performed as necessary.

\*2: The first day of the treatment period is the day that investigators/subinvestigators determine the subject is eligible to begin treatment.

\*3: Fundoscopy and chest X-ray to be performed to extent possible within 14 days of study withdrawal.

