### 9.2.2 Treatment status

During the treatment period, investigators/subinvestigators or clinical coordinators will ask subjects about the following information, to be recorded in CRFs.

- 1) MT-6548 dosage (details and reasons for change if there was a change of dosage or drug holiday)
- 2) First day of MT-6548 treatment and final day of MT-6548 treatment
- 3) MT-6548 treatment compliance status
- 4) Timing of MT-6548 doses (pre-prandial: within 30 minutes prior to eating; post-prandial: within 30 minutes of eating (including eating); other)
- 5) MT-6548 dose date and time\*

\* Date and time of dose immediately prior to blood sampling for EPO measurement at treatment period Weeks 2, 4, 6, 12, 24, and day of discontinuation.

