### 12.2 Procedures for withdrawal

If a subject withdraws from the study, the investigator/subinvestigator will take all appropriate actions toward the subject, immediately inform the study monitor of the withdrawal, and notify the study sponsor by fax according to “8.2.4 Withdrawal processing.” If a subject withdraws from the study, investigators/subinvestigators will perform all tests required at discontinuation within 7 days of discontinuation (fundoscopy and chest X-rays are to be performed to extent possible within 14 days of discontinuation).

Investigators/subinvestigators will record date of withdrawal and reasons for withdrawal in the CRF for subjects who withdraw from the study following the first day of the treatment period. If the reason for withdrawal is an AE, the name of the event will be recorded in the CRF. The date of evaluations performed upon withdrawal is used as the date of withdrawal, but if these evaluations

could not be performed, the date of determination of withdrawal may be used instead. If tests and observations required on the day of withdrawal cannot be performed for a given subject, or the subject does not make any post-withdrawal visits, follow-up investigation will be performed through correspondence (sealed letters) or telephone to ascertain reasons for this and subsequent course, and information obtained recorded.

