## 4.10 Mean daily dose

Mean daily dose of MT-6548 during each scheduled study visit period\* = Daily dose based on the physician's prescription × Period of administration (days)\*3 of the corresponding dose\*2 between the scheduled study visits\* / Period between the scheduled study visits (days)\*4

\*: For each period between the scheduled study visits, the actual study visit dates will not be considered, and this variable should be fixed as follows:

- ✓ The first day of the treatment period to Week 2 of the treatment period: The first day of the treatment period (Day 1) to Day 14
- ✓ Week 2 of the treatment period to Week 4 of the treatment period: Day 15 to Day 28
- ✓ The same shall apply thereafter, and the final period between the scheduled study visits should be Week 20 to Week 24 of the treatment period: Day 141 to a blood sampling day for hematological tests at Week 24 of the treatment period.

However, for subjects who discontinued their treatment, the final period between the scheduled study visits should be up to the day before discontinuation.

\*: If there are multiple applicable doses, the sum of the calculated values for each dose should be used.

\*: The number of days without drug administration other than drug interruption should not be excluded from the "period of administration (days)".

\*: 14 days up to Week 12 of the treatment period and 28 days after Week 12 of the treatment period. However, for subjects who discontinued their treatment, the final period between the scheduled study visits (days) should be the actual number of days until the day before discontinuation.

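### End dates for exposure and compliance do not align: SAP 4.6 closes an open interruption one day early, and SAP 4.7 ends early stoppers' exposure at an undefined day instead of the last dose

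*SAP*

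**What the plan says.** **Duration (SAP 4.7).** For completers: "Duration of study drug administration (days) = Day of blood sampling for hematology tests at Week 24 – First day of the treatment period". For subjects who stop early: "Duration of study drug administration (days) = Day of discontinuation – First day of the treatment period". The SAP does not define the day of discontinuation.

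**Interruptions (SAP 4.6).** Interruption days are the resumption day minus the first interruption day. For an interruption still open when treatment is discontinued, 4.6 closes it so that "the day before the discontinuation of treatment should be used". The SAP errata moves the matching date for completers to the day before the Week 24 haematology sampling. In the available text the added words carry a strike-through mark. The errata gives an omission as its reason, and the sentence does not parse without those words, so they are read here as an insertion.

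**Derived quantities.** SAP 4.8 subtracts missed days and interruption days from the period to give administration days. SAP 4.9 divides those days by the period less interruption days. SAP 4.10 ends the last dosing interval the day before discontinuation and adds that "The number of days without drug administration other than drug interruption should not be excluded".

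**Protocol dates.** Section 8.4 sets dosing "From the first day of the treatment period to the day prior to Week 24 of the treatment period". Section 9.2.2 records "First day of MT-6548 treatment and final day of MT-6548 treatment". In Table 9.1-1 (section 9.1) the discontinuation visit is allowed "Within 7 days of discontinuation". Section 12.2 states: "The date of evaluations performed upon withdrawal is used as the date of withdrawal".

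**The concern.** Subtracting two dates counts days correctly only if the later one is the first day no longer counted. For completers SAP 4.7 meets this condition, because planned dosing stops the day before Week 24. Two places do not secure it.

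First, 4.6 closes an open interruption one day before the period in 4.7 ends. The last off-drug day then belongs to the period but not to the interruption, and 4.8 credits it as a dosing day.

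Second, for early stoppers 4.7 relies on a day that the documents allow to be either the stopping date or the evaluation visit up to a week later. The recorded last dose would settle this, but 4.7 does not use it. Two programmers could derive different exposure from the same data. How the off-drug days then affect compliance depends on CRF coding that the SAP does not specify.

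At stake are the duration, mean daily dose, cumulative dosage and compliance summaries (SAP 8.4 and 8.5.2), including the split at 80% compliance. The subjects affected are those who stop early or end treatment while off drug, whose exposure is of most interest when safety is read.

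**Working it through.** The plan states no figure of its own for this point, so its formulas are applied directly. Day numbers follow protocol Table 9.1-1 (first day = Day 0, Week 24 = Day 168).

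**1. Interruption open at the end (SAP 4.6 with the errata).** Dosed Days 0–160 (161 days), off drug Days 161–167 (7 days), Week 24 sampling on Day 168.

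- Duration (4.7): 168 − 0 = 168.
- Interruption days (4.6): 167 − 161 = 6. True value: 7.
- Administration days (4.8), no missed doses: 168 − 0 − 6 = 162. True value: 161.
- Compliance (4.9): 162/(168 − 6) = 100%. With the right dates: 161/(168 − 7) = 100%.

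The error is one day per open interruption. An interruption that begins on Day 167 counts as 167 − 167 = 0 days. Compliance does not move for an otherwise adherent subject, because the extra day enters numerator and denominator alike.

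**2. Which date is the day of discontinuation?**

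| Supports the evaluation date | Supports the stopping date |
|---|---|
| SAP 2.2 schedule: it is a visit column (TV11) with its own permitted range | Protocol Table 9.1-1: it is the reference date from which the visit window runs |
| Protocol 5.2(2): the treatment period ends with blood sampling on the final day | Protocol 12.2: discontinuation tests follow within 7 days of discontinuation |
| Protocol 9.2.3: sampling is scheduled on the day itself | |
| Protocol 9.2.4.2 equates stopping drug with study withdrawal, and 12.2 dates withdrawal at the evaluation | |

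Both readings are open.

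**3. Size on the evaluation-date reading.** Let D be days dosed with no missed dose (Days 0 to D − 1) and k the off-drug days before the date used. Duration is D + k. Compliance depends on how the k days are coded:

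- Not entered: 100%.
- Entered as 0 mg: with k = 7, 4.6 removes (D + 6) − D = 6 days, leaving a denominator of D + 1. Compliance is 100%, or D/(D + 1) if the leftover day is counted as missed.
- Entered as missed doses: D/(D + k).

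With k = 7:

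| D | Duration | Overstatement (7/D) | 0 mg coding, lower value | Missed-dose coding |
|---|---|---|---|---|
| 14 | 21 | 50.0% | 93.3% | 66.7% |
| 27 | 34 | 25.9% | 96.4% | 79.4% |
| 28 | 35 | 25.0% | 96.6% | 80.0% |
| 84 | 91 | 8.3% | 98.8% | 92.3% |
| 140 | 147 | 5.0% | 99.3% | 95.2% |

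Under missed-dose coding, D/(D + k) < 0.8 when D < 4k: fewer than 28 dosed days for k = 7, 12 for k = 3 and 4 for k = 1. If the last dose was taken on the stopping day itself, the largest excess is 6 days.

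**4. Last-interval dose (SAP 4.10), same reading.** Take 300 mg for 7 days followed by 7 off-drug days. Coded as missed doses, the interval mean stays at 300 mg. Coded as 0 mg, it is 300 × 7/14 = 150 mg.

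**5. Whole-trial effect.** The documents do not give the number of discontinuations. Assume 40 subjects, m early stoppers dosed 84 days each, k = 7 and 168 days for the rest. Total exposure is overstated by 7m/[(40 − m) × 168 + 84m]: 0.2% for m = 2 (14/6552), 0.4% for m = 4 (28/6384), 0.9% for m = 8 (56/6048) and 1.5% for m = 12 (84/5712).

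**The case against.** **The evaluation-date rule is written for withdrawal, not discontinuation.** Protocol 12.2 gives the evaluation date to withdrawal, while Table 9.1-1 and the same section 12.2 start the 7-day window at discontinuation. On that reading, with the last dose the day before, 4.7 is exact and matches the completer rule. This stands. A reader might infer that the protocol places the day of discontinuation at the evaluation visit, but the documents do not settle that. What remains is an undefined term with two supported readings.

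**Off-drug days need not become missed doses.** SAP 4.6 provides for treatment that ends during an interruption. Days entered as 0 mg leave the compliance denominator almost entirely and add no dose in 4.10. This also stands. Two stronger readings are therefore unsupported as general statements: that any adherent subject who stops before Day 28 is reported below 80%, and that the last interval always counts off-drug days at the prescribed dose.

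**The one-day error in 4.6 is small.** It is, and it leaves compliance at 100% for an otherwise adherent subject. It is nonetheless a stated rule that miscounts, and it does not depend on how the day of discontinuation is read.

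**The outputs are secondary.** Agreed. SAP 8.4 plans descriptive summaries without confidence intervals. Compliance defines neither analysis set (SAP 5.1, 5.2) and does not enter the Hb model (SAP 8.5.1).

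**Conclusion.** The point holds in two parts of different strength.

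1. **Certain.** SAP 4.6 with the errata and SAP 4.7 use end dates one day apart. Each interruption open at the end of treatment is counted one day short, and 4.8 credits one dosing day that did not occur. For discontinued subjects this follows from the SAP body text alone; for completers it follows from the errata as read above.
2. **Conditional.** SAP 4.7 does not tie early stoppers' exposure to the recorded last dose. If the day of discontinuation is the evaluation date, duration is overstated by up to 7 days. Compliance is then unaffected, nearly unaffected or lowered according to coding. Falling below 80% needs the evaluation-date reading, missed-dose coding and fewer than 28 dosed days with the full 7-day gap. If that did happen to one of 40 subjects, the proportion at or above 80% would move by 1/40 = 2.5 percentage points.

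On the assumptions shown, total exposure shifts by 0.2% to 1.5%, so the effect lies with individual early stoppers rather than the trial total. A reader might infer that the efficacy result is at risk; nothing in the plan supports that. The fault is confined to descriptive exposure, dose and compliance outputs. It is worth correcting because the correction is specific and nearly free.

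**What to change.** Define one exclusive end date E in SAP section 4, meaning the first day no longer counted:

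- discontinued subjects: E = recorded final day of MT-6548 treatment + 1;
- completers: E = Week 24 haematology sampling day.

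Then:

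- **4.7:** duration = E − first day of the treatment period. Use the same name for this period in 4.8 and 4.9.
- **4.6 and the errata:** close any open interruption at E. An off-drug period that starts at or after E counts as 0 days. This clause is needed: closing the interruption at the final dosing day itself would give −1 day when it starts the day after the last dose.
- **4.10 and 4.11:** end the last interval and the last dose period on the day before E. SAP 4.11 currently gives no end date for a final dose that is never changed.

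Check: the completer in step 1 gets 168 − 161 = 7 interruption days and 161 administration days. A subject dosed Days 0–13 who then stops has E = 14, a duration of 14 days and 100% compliance, whenever the evaluation took place.

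One consequence should be stated in the SAP: an interruption that runs straight into discontinuation adds no days in 4.6, whereas one that runs into Week 24 still does. Administration days and compliance are right in both cases.

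The cost is SAP and errata wording and minor reprogramming. The final dosing day is already collected, so no new data are needed.
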